Diagnosis of RDS will be based on⁵ (i) presence of at least two of four classic symptoms (need of supplemental O₂, tachypnea, intercostal retractions or grunting), *and* (ii) exclusion of other causes of respiratory failure, *and* (iii) Clinical team plan to administer surfactant if infant requires intubation. A chest x-ray (CXR) is not mandatory prior to enrollment; however, if obtained clinically, severity of RDS will be graded and results recorded (Appendix VII [Table A4])⁶. We have not mandated a radiologic diagnosis of RDS because classic radiologic findings may evolve over the first 12-24 hours and be modified by early NIV; furthermore, the need for a CXR may unnecessarily delay study intervention^{7,8}.

1.1.4.2. Timing of Aerosolized Surfactant:

Enrolled infants will receive AS at ≤ 24 hours of age & within 8 hours of initiating NIV as several studies have shown that earlier administration of surfactant to PT babies with RDS improves outcomes.

1.1.4.3. Study Intervention – Aerosolized Surfactant Preparation and Dose:

For this study, Survanta (200 mg PL/8 ml) (Beractant, Abbvie Inc.) will be used at two doses – 100 mg/kg and 200 mg/kg and two dilutions (1:1 and 1:2) resulting in 4 dose schedule groups.

Survanta has been chosen as the surfactant for this study as this is the surfactant used exclusively at our institution; it is also the most commonly used surfactant with the longest duration of use in the US^{9,10}. *We will validate aerosolized use of other surfactants in subsequent studies.* Many studies have compared Survanta with other animal derived surfactants, however, consensus regarding the best preparation has yet to be determined¹⁰. Although several relatively small randomized controlled trials (RCTs) showed significant reductions in mortality and need for redosing with high-dose (200 mg/kg) but not low-dose (100 mg/kg) poractant alfa vs. beractant (100 mg/kg)^{11,12}; three large recent retrospective cohort studies of surfactant use in the US (n=51,282 and 14,173) and Australia (n=515) published in 2013 failed to show significant differences in outcome between poractant and beractant in PT neonates with RDS^{9,13,14}. It is speculated that previously described differences in mortality between surfactants may relate to site variation in outcomes⁹.

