Only short binasal prongs will be used for aerosol delivery in the NIV circuit. Since the ventilator circuit for NCPAP and NIPPV is identical, only one type of neonatal nasal prongs (INCA®) will be used. For the HFNC circuit, only the neonatal Fisher & Paykel short binasal prongs will be used. Nasal cannulas will be applied with recommendations that the prong outer diameter occupy $\sim 50\%$ of the nares internal diameter to allow free egress of flow around the cannula³⁴.

d) Number of doses of Aerosolized Surfactant & Intervals between Doses:

Infants will be eligible to receive a 2nd dose of AS 4 hours after the 1st dose of AS if there is continued need for NIV with FiO₂ $\geq 25\%$ or PEEP ≥ 4 cmH₂O or HFNC rate ≥ 2 LPM.

Since most PT infants with RDS receive ≤ 2 doses of intratracheal surfactant as standard of care, we chose 2 doses of AS as being the minimum number to assess efficacy without inordinately delaying standard of care treatment with intratracheal surfactant⁵⁸. Early trials of intratracheal surfactant used dosing intervals ranging from 1 to 12 hours based on ventilator settings. Since pulmonary delivery following aerosolisation is not precisely quantified, we will administer the 2nd dose 4 hours after the 1st if the infant meets criteria.

e) Duration of nebulization:

Time to nebulize each dose will depend upon volume of diluted surfactant, type of nebulizer, and ambient humidity and temperature. It is expected that for each dose nebulization will be <1 hour for the smallest infants and $<4-5$ hours in the largest infants. This Phase II study will provide critical information regarding time for nebulization of various doses for PT babies and will be crucial in determining tolerance of intervention both by the patient and clinical bedside caregivers. This will be one factor in selecting the optimal dose and dilution of AS for the definitive Phase III trial.

1.1.4.5. Gestational Age Group Strata:

Enrolled infants will be stratified by three GA strata (24^{0/7}-28^{6/7}; 29^{0/7} - 32^{6/7}, 33^{0/7} - 36^{6/7}) because need for intubation and MV has been reported to be higher in more immature infants along with higher co-morbidities of prematurity and mortality. Infants <24 weeks will be excluded as most are likely to receive intubation. ^{59,60}

1.1.4.6. Randomization Procedures: Assignment to Surfactant dosing schedule:

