An *a priori* computer-generated stratified block randomization list will be used to assign patients to each of the 4 parallel fixed dosing schedules (allocation ratio 1:1:1:1, total subjects = 120). To ensure randomization of equal number of subjects to both nebulizers, block size of 8 will be used. To ensure equitable representation of gestational ages, GA stratum-specific randomization lists will be generated. Stratified block randomization will ensure balanced and independent distribution of participants within each dose group, avoid systematic differences between dose groups with respect to known or unknown confounding baseline variables, remove selection bias and control temporal trends^{2,62-66}. The balance resulting from blocked stratification can improve the power of trials by reducing unwanted variation, reduce Type I and II error rates, increase efficiency, and improve subgroup analyses.

The structure of Table 10 shows breakdown of the sample by confounding variables in rows (GA [stratifying factor] & nebulizer type [blocking factor]) with columns representing treatment groups. Therneau showed that balance in covariates begins to fail when the number of blocks approaches half the sample size (n/2)^{64,67}. Therefore studies using stratified assignment should not attempt to balance on

Table 10: Stratified Block Randomization of Sample

GA Group (Strata)	Nebulizer Device (Blocks)	Dosing Schedule			
		I	II	III	IV
24 0/7 – 28 6/7 (Extremely PT) ⁶¹	MiniHeart	5	5	5	5
	AeroNeb	5	5	5	5
29 0/7 – 32 6/7 (Very PT)	MiniHeart	5	5	5	5
	AeroNeb	5	5	5	5
33 0/7 – 36 6/7 (Moderately PT)	MiniHeart	5	5	5	5
	AeroNeb	5	5	5	5
Total		30	30	30	30

more than 2 to 3 important factors. In this study we have balanced 2 important factors (GA, nebulizer type); the resulting number of blocks (3 GA strata x 2 nebulizers x 4 dosing schedule groups=24) is <n/2 (120/2=60).

Multiple births, common in this premature population, will be randomized independently and not as a unit as the latter can lead to bias in the randomization process.

1.1.4.7. Allocation Concealment:

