In this safety, feasibility and dose finding Phase II trial, 30 infants will be assigned to each of the 4 dose schedules^{4,88}. The aim of phase II trials is to explore different doses, evaluate safety & tolerability, and obtain early indication of efficacy⁸⁸. The dose-safety relationship is more important than the dose-efficacy one as efficacy is irrelevant if the dose is unsafe⁸⁹. Phase II trials are generally inadequate with respect to size, outcome, precision, and control of bias to provide formal proof of efficacy^{3,90}. Rather these trials provide baseline data, potential primary outcome and effect size justifying the larger, longer, and more expensive Phase III trial. *Recognizing that our Phase II trial is not powered for efficacy, sample size calculations based on precision of the estimate of the primary outcome & the null hypothesis and error rate are presented below.*

Sample Size Based on Precision for the Primary Efficacy Outcome:

The efficacy goal of Phase II studies is typically to estimate a clinical endpoint with a specified precision. The primary efficacy outcome in this study is the need for intubation & MV within 72 hours of AS. Using the normal approximation to the binomial as described by Piantadosi⁸⁸ ($w = Z_{\alpha} \times \sqrt{p(1 - p)/n}$; or more simply $n=1/w^2$ for estimated proportions (p) ranging from 0.2 to 0.8, where Z_{α} is the quantile from the normal distribution corresponding to the two-sided probability, n =sample size, w =width of the 95% confidence interval [CI] or precision), a sample size of 30 per dosing schedule group will allow evaluation of a failure rate of 0.25 - 0.4 with 95% CI of ± 0.15 to ± 0.17 (15 to 17% precision) (Table 12). The precision of this estimate is increased if we collapse the dilution groups corresponding to dose of 100 mg/kg & 200 mg/kg (<12%) or consider our entire sample of 120 subjects all of whom receive the study intervention (<9%).

Table 12: Sample Size & Precision for various proportions of primary efficacy outcome:

Sample Size	Rate	Precision for Estimating Outcome		
		95% CI		Precision
		Lower	Upper	
30 (for each dosing Schedule i.e. I, II, III, IV)	0.25	0.13	0.43	$\pm 15\%$
	0.3	0.17	0.48	$\pm 15\%$
	0.35	0.21	0.53	$\pm 16\%$
	0.40	0.25	0.58	$\pm 17\%$
60 (for each dose group 100/kg vs. 200 /kg)	0.25	0.16	0.37	$\pm 11\%$
	0.3	0.2	0.45	$\pm 12\%$
	0.35	0.24	0.48	$\pm 12\%$
	0.40	0.29	0.53	$\pm 12\%$
120 (for the whole group)	0.25	0.18	0.33	$\pm 8\%$
	0.3	0.23	0.39	$\pm 8\%$

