Table 13: Power for a Test of the Null Hypothesis assuming a Historical Control Value of 0.5

Sample Size	Rate	Absolute RR	Relative RR	Power
30 (for each dosing Schedule I, II, III, IV)	0.25	.25	.50	81.8%
60 (for each dose group 100/kg vs 200 /kg)	0.25	.25	.50	98.2%
	0.3	.2	.40	89.0%
120 (for the whole group)	0.25	.25	.50	99.9%
	0.3	.20	.40	99.5%
	0.35	.15	.30	91.6%

Power is for a two sided test with Type I error of 0.05

After enrollment of 32 infants in the Phase II study, it was recognized that there was difficulty in recruiting infants in the lowest GA stratum. The data monitoring committee (DMC) recommended:

- a. Re-distribution of sample size for the study (n=120) between the two higher GA strata (60 infants per stratum compared to previous sample size of 40 infants per stratum). This will allow retention of power of the sample size calculations in the original proposal for analysis in the margins.
- b. Aim to enroll additional 10-20 at least (maximum 40) patients in the lowest GA stratum to address feasibility of study intervention in this group and generate hypothesis for effect size estimate for efficacy in this stratum.

On July 21, 2016, we submitted a clarification amendment to the IRB requesting continued enrollment in Stratum I upto a maximum of 40 subjects as originally proposed till the enrollment targets for the higher two GA strata were met (approved 07-29-2016). This was based on our enrollment patterns, making it seem unlikely that we would reach our enrollment targets ahead of the timeline (30-36 months for study accrual) in the three GA strata.

In Dec 2016, we attained accrual goals for the two higher GA strata. We observed a change in enrollment patterns in the last 5 months of 2016 - we were able to enroll more infants overall and specifically more infants in Stratum I. Since we had several more months available for patient accrual on this grant, we requested an amendment allowing us to continue enrollment in the lowest stratum till Dec 09, 2017 for a maximum of 40 subjects in this stratum, whichever comes earlier. Since Stratum I subjects are most likely to benefit from this intervention, having as much data as possible about feasibility and efficacy in this GA group will be valuable in designing the future definitive Phase III randomized controlled trial.

This amendment was discussed with the FDA grant officer who recommended (02-17-2017) proceeding with amendment submission to IRB and IND review Division if the DMC concurs.

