Data will be analyzed according to the intention-to-treat principle using SAS and PASW (IBM Inc.). We will report descriptive statistics for demographic, clinical and respiratory support data at baseline and over time for the entire sample and for the 4 dosing schedule groups (Appendix IX [Table M1, M2]). In addition, three subgroup analyses are planned – according to dose regardless of dilution (100 vs. 200 mg/kg), GA strata, nebulizer device using logistic regression incorporating an additional treatment-by-subgroup interaction term.

Analysis plan to address Aim #1 – Safety and Feasibility Assessment: Safety will be assessed by quantifying and comparing the AEs and their severity for the total sample and across the dosage/dilution groups and two types of nebulizers. Indicators include cardiorespiratory responses, blockage of NIV circuit and cerebral oxygen saturation (Appendix IX [Table M5]). Descriptive statistics (mean, standard deviation, proportion, inter-quarter range [IQR]) will be used to quantify these indicators; *confidence intervals will be preferred to hypothesis testing* as considerable imprecision is expected arising from low frequencies of these AEs³. ANOVA or *t*-test (continuous measures) and χ^2 test (categorical variables) will be used for comparative analyses though we may not find statistically significant differences. Paired *t*-test will be used to compare heart rate, respiratory rate, blood pressure, SpO₂, PCO₂, cerebral oxygenation (RCO₂, cFTOE), ACoRN score and nasal exam score before and after AS. These parameters will also be compared between infants who get intubated within 72 hours of study intervention and those who do not; and before and after intubation within subjects that get intubated. Feasibility will be assessed by quantifying and comparing the percentage of infants who tolerate the treatment procedure and responses of the clinical nurses and respiratory therapists on the feasibility questionnaire (Appendix IX [Table M6]). Because of the high inherent variability of these factors and small effect sizes, we do not expect to show significant differences between groups given our sample size. However this information will be useful in making the final decision to proceed with a Phase III RCT.

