Analysis plan to address Aim #2: - Determination of Optimal Dilution and Dosage of AS: The optimum dose is one that produces low toxicity while nearly maximizing the biological response⁸⁹. The optimal dosage will be determined by comparing levels of adverse responses, feasibility items and primary and secondary efficacy treatment outcomes (rates of intubation, diagnosis of PDA, need for blood transfusions, postnatal growth, duration of respiratory support, length of hospital stay, and incidence of complications of prematurity including IVH, sepsis, pneumonia, BPD, NEC, ROP, and death) across the four dosing schedules (Appendix IX, Mock Tables). The optimal dosage/dilution will be the one with the minimum level of adverse responses and highest clinical treatment outcomes.

Analysis plan to address Aim #3 - Short-term efficacy of AS: The primary outcome variable for short-term efficacy is the need for intubation & MV within 72 hours of AS. We will estimate the unconditional probability of benefit for the four dosing schedule groups (I, II, III, IV), the 2 dose groups (100 vs. 200 mg/kg) and the entire study cohort of 120 subjects. We will also compare with reported rates of intubation in historical controls (50%). A special χ^2 test to compare sample proportion with population proportion will be conducted to test the study hypothesis that AS is efficacious. In the comparison analysis, different dosages/dilutions will also be considered as weight using the “optimal” dosage/dilution obtained from Aim #2 as reference. A significantly lower rate of intubation in infants treated with AS in this study as compared to the reported rate of ~0.5 at $p < 0.05$ level (two-sided) will be used as evidence supporting the efficacy of AS. However, it is likely we may not

have power to achieve statistically significant results. Nevertheless these preliminary efficacy data will be crucial in determining outcome measures and effect size for the definitive placebo-controlled Phase III trial.

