A number of secondary outcomes will be assessed using the same methodology. Vital signs, SpO₂, FiO₂, NIV parameters (pressure, rate, flow) and ABG/CBG components (pH, PO₂, PCO₂) will be evaluated before and after study intervention (paired *t*-test) and over time (Longitudinal data analysis). Other secondary outcomes include change in surfactant activity in gastric aspirates, changes in cerebral oxygenation, diagnosis of PDA, need for blood transfusions, postnatal growth, duration of respiratory support, length of hospital stay, and incidence of complications of prematurity including IVH, sepsis, NEC, BPD, pneumonia, ROP, and death. We will describe and compare primary and secondary outcome data overall and by dosing schedule, and in three pre-planned subgroup analyses – by dose regardless of dilution (100 mg/kg vs 200 mg/kg), GA group stratum and nebulizer type, recognizing that we may observe trends of differences between groups without having power to determine statistical significance. We will report dichotomous secondary outcome data as proportions and compare the groups using χ^2 and nonparametric tests. We will report secondary continuous outcome data as mean (SD) for normally distributed data and median (interquartile range [IQR]) for skewed data, and will compare the groups by using parametric (*t*-test, ANOVA) and nonparametric tests (Mann-Whitney U test, Wilcoxon's test) as appropriate. Pairwise group comparisons of the four dosing schedule groups will also be performed, although we may lack power to detect significant differences. In a final posthoc analysis, we will compare infants who received intubation within 72 hours to those who did not to understand risk factors for intubation and their modification by study intervention. This analysis will be presented for the entire group and by dosing schedule group. In *adjusted analyses*, dosing schedule, GA group, nebulizer type, mode of NIV, antenatal steroids, and presence of PDA or IVH will be included as covariates recognizing that these analyses are exploratory and need to be interpreted cautiously. We will consider a p value of <0.05 for statistical significance. Mock tables for the planned analyses are presented in Appendix IX.

Recommendations for statistical analyses by the Data Monitoring Committee (DMC) during the conduct of the trial:

1. Additional factors associated with intubation in enrolled infants – clinical team, time of day/shift, clinical variables (e.g. sepsis, NEC)

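### Aim #2 asks for the optimal dilution, but the analysis text pre-specifies a pooled comparison only for dose and no main effect of dilution

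*Combined protocol and SAP*

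**What the plan says.** **Design.** Section 1.1.4.3 crosses 100 and 200 mg/kg with "two dilutions (1:1 and 1:2) resulting in 4 dose schedule groups". Section 1.1.4.6 allocates equally ("allocation ratio 1:1:1:1, total subjects = 120"), and section 1.1.10 puts 30 infants in each schedule.

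**Objective.** In section 1.1.12, Aim #2 is titled "Determination of Optimal Dilution and Dosage of AS". Section 1.1.4.4(e) says of nebulization time: "This will be one factor in selecting the optimal dose and dilution of AS for the definitive Phase III trial".

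**Where dose is pooled over dilution.**
- The subgroup analyses in 1.1.12: "according to dose regardless of dilution (100 vs. 200 mg/kg), GA strata, nebulizer device" at the start of the section, and later "by dose regardless of dilution (100 mg/kg vs 200 mg/kg), GA group stratum and nebulizer type".
- The Aim #3 estimates: four schedules, two dose groups and the whole cohort.
- Tables 12 and 13 in 1.1.10, where the middle block of Table 13 is labelled "60 (for each dose group 100/kg vs 200 /kg)".

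**Where dilution enters.** Only inside the four-level schedule: the Aim #2 comparison across schedules, the pairwise schedule comparisons (which include I v II and III v IV), and schedule as a covariate in the adjusted analyses. The safety plan refers to dosage/dilution groups without defining a pooled dilution group. The supplied text has no I+III v II+IV comparison, no separate dilution term and no dose-by-dilution estimate.

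**The concern.** The design randomizes two factors and the objective names both, but only one gets the more precise comparison that a 2x2 allows. Section 1.1.10 itself argues that collapsing groups improves precision, and applies this to dose and to the whole cohort but not to dilution.

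The protocol gives reasons to expect dilution to matter. Section 1.1.4.4(a) says clogging of the vibrating-mesh nebulizer can be relieved by more dilute surfactant, and 1.1.4.4(e) makes nebulization time depend on diluted volume. What is at stake is the precision with which a dilution is chosen for Phase III. Without a stated margin, that choice would be read from two separate 30 v 30 contrasts, or from a global test that does not say how far the dilutions differ.

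**Working it through.** **Inputs from the documents.** Four schedules of 30 (N = 120); two-sided alpha 0.05; Table 13 power of 81.8% for n = 30 and a rate of 0.25 against 0.5; amended Phase II total of 220, including 20 for screen failures (1.1.10).

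**Assumptions.** The documents give no expected difference between dilutions, so the event rates for dilution contrasts are illustrative. For the amended size I assume 220 − 20 = 200 infants analysed, 50 per schedule.

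**Step 1. The plan's own figure.** One-sample arcsine formula: power = Φ(2·|asin√0.5 − asin√0.25|·√n − 1.96). With n = 30: Φ(0.5236 × 5.477 − 1.96) = Φ(0.908) = 81.8%. This reproduces Table 13. It concerns one schedule against a fixed 0.5, not a contrast between dilutions.

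**Step 2. Precision of a dilution difference.** Half-width = 1.96·√(2p(1−p)/n), with n per group.

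| Common rate | One pair, 30 v 30 | Pooled over dose, 60 v 60 |
|---|---|---|
| 0.25 | ±21.9 points | ±15.5 |
| 0.30 | ±23.2 | ±16.4 |
| 0.40 | ±24.8 | ±17.5 |

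At 0.30: 1.96·√(0.42/30) = 0.232 and 1.96·√(0.42/60) = 0.164, a ratio of √2. With 200 analysed: ±18.0 (50 v 50) against ±12.7 (100 v 100).

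The equal-weight average of the two within-dose contrasts has SE √((0.118² + 0.118²)/4) = 0.084, the same as the pooled contrast. So the information is collected; the plan does not say to combine it.

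**Step 3. Power for a pure dilution effect, N = 120.** Pair and pooled: two-proportion z-test with the pooled SE under the null. Four-group χ²: 3 df, noncentrality λ = 30·Σ(pᵢ − p̄)²/[p̄(1 − p̄)]. For 30% v 10%, p̄ = 0.20 and λ = 30 × 0.04/0.16 = 7.5.

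| Rates | One pair | Four-group test, 3 df | Pooled |
|---|---|---|---|
| 30% v 10% | 49% | 62% | 79% |
| 40% v 20% | 39% | 50% | 67% |
| 50% v 25% | 52% | 65% | 82% |

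With 200 analysed, 30% v 10% gives 71%, 86% and 95%. For a smaller difference, 40% v 25% at N = 120, pooling raises power only from 23% (one pair) to 42%.

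**Step 4. How well interaction can be checked.** The half-width for the difference of the two dilution differences is 1.96·√(4p(1−p)/30). At p = 0.30 this is 1.96·√(0.84/30) = 0.328, about ±33 points.

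**Step 5. Is interaction plausible?** From the schedules in 1.1.4.3, total volumes are 4+4 = 8, 4+8 = 12, 8+8 = 16 and 8+16 = 24 ml/kg. Going from 1:1 to 1:2 adds 4 ml/kg at the lower dose and 8 ml/kg at the higher. If nebulization time follows volume, the absolute effect of dilution on time differs by dose.

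**The case against.** A reader might infer that dilution is never analysed, or that half the randomized data are thrown away for that question. The documents do not support this. The four-schedule comparison uses every infant, I v II and III v IV together use every infant, and a dilution contrast could be derived from the schedule covariate. What is missing is a pre-specified combined estimate.

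Four further points stand in part.
- **Comparator.** Setting the pooled test only against one pair overstates the gain. For 30% v 10%, the gain over the four-group test is about 17 points of power (62% to 79%), not 30. That test still yields no dilution estimate or interval.
- **Purpose.** Aim #2 chooses the schedule with the fewest adverse responses and best outcomes, and 1.1.12 prefers intervals to tests for safety. Interval width is therefore the fairer measure of the gain; power is secondary.
- **Clogging.** Section 1.1.4.4(a) attributes it to the mesh device, which Table 10 gives to half the infants (15 per schedule). On that device alone the pooled contrast is 30 v 30, so the 79% does not apply to it.
- **Interaction.** Steps 4 and 5 show that it is plausible for nebulization time and only weakly checkable. Comparing whole schedules is thus defensible. But the planned dose margin averages over dilution on the same footing, and no dose-by-dilution check is planned for it.

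**Conclusion.** The point holds as a gap in pre-specification. Aim #2 names dilution, the design supports a dilution main effect, and the supplied analysis text provides the pooled margin for dose only. The cost is precision: about ±23 against ±16 points at a 30% rate with 120 infants, or ±18 against ±13 if 200 are analysed. The rates are illustrative, and the 200 and its equal split are assumptions. The gain is modest for small effects, and group differences may still not reach significance, as the plan itself says.

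The Appendix IX mock tables are not in the supplied text. They may show a dilution margin, although the two lists of three subgroup analyses in 1.1.12 do not. This is a cheap improvement to an exploratory phase II analysis, not a flaw that invalidates it.

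**What to change.** In section 1.1.12:

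1. Add dilution regardless of dose (I+III v II+IV), stratified by dose, as a pre-planned comparison with its 95% CI for safety, feasibility and the primary efficacy outcome.
2. Report the dose-by-dilution estimate with its CI, stating that it will be imprecise (about ±33 points at N = 120 and a 30% rate) and that a non-significant result does not establish absence of interaction.
3. Under Aim #2, say that the dilution margin will be read alongside the four-schedule results when the optimal dilution is named. For nebulization time, show the within-dose contrasts as well.
4. Check that the Appendix IX mock tables carry the dilution margin, and add it if they do not.

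The cost is a few lines of SAP text and possibly some table rows, with no new infants or data. The downsides are one more comparison in an exploratory set and a margin that can mislead if dose and dilution interact, the same risk as in the dose pooling already planned.

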- ii). Secure cooperation of clinical bedside nurses and respiratory therapists in administering aerosol.
- iii). Identify and randomize a sufficient number of patients within a reasonable study period. This includes ability to identify eligible infants, obtain informed consent, and prepare and deliver aerosolized study medication in the defined time frame.

1.1.7.3. Dose Finding:

We will randomize infants to receive one of 4 fixed dosing schedules. Data collected during this Phase I/II trial will be critical in selecting the optimal dosing schedule for the definitive Phase III trial. Optimal dosing schedule will be determined by preliminary evidence of efficacy, lack of adverse effects, and tolerance by patients and bedside clinical caregivers.

1.1.7.4. Efficacy:

The primary efficacy outcome for this Phase I/II trial is the need for need for intubation and MV within 72 hours of study intervention (treatment failure). This will be compared to a historical control rate of 0.5 for need for intubation in PT infants 24-36 weeks GA undergoing NIV. Treatment failure criteria are defined *a priori* in Section 3.6.5. We chose treatment failure within 72 hours of randomization as our primary efficacy outcome as failure within that time would likely be due to RDS, whereas failure after this time would more likely be due to secondary causes like sepsis, PDA, pneumonia, NEC, IVH, or apnea of prematurity.

1.1.8. Secondary Efficacy Outcomes:

1. CBG/ABG, pulse oximetry, vital signs at 60±30 minutes after end of AS
2. Number of doses of surfactant – aerosolized & intratracheal
3. Respiratory support at 24, 48 & 72 hours, 7 days (D7), D14, D28, 36 weeks corrected GA and Discharge.
4. Pneumothorax, pneumomediastinum or other air leak
5. Changes in cerebral oxygenation as evaluated by NIRS
6. Changes in surfactant activity in gastric aspirates
7. Cumulative duration of NIV and invasive ventilation on D3, D7, D14, D28, 36 weeks CGA and discharge
8. Duration of supplemental oxygen, intensive care, hospital stay
9. Age at start of feeds, feeding progression, age at full enteral feeds
10. Need for blood transfusions
11. Growth parameters at 7 days, 28 days, 36 weeks corrected GA and discharge
12. Morbidities associated with prematurity: PDA, IVH (Grade III-IV), NEC, periventricular leukomalacia, ventriculomegaly, ROP (stage>3 or requiring treatment), and BPD. Two definitions of BPD will be used:

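### The logistic subgroup interactions do not define the treatment contrast and make no provision for empty cells; if the contrast is the four schedules, some schedule-by-GA estimates may be infinite.

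*Combined protocol and SAP*

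**What the plan says.** Section 1.1.12 plans three subgroup analyses: by dose irrespective of dilution, and by "GA strata, nebulizer device using logistic regression incorporating an additional treatment-by-subgroup interaction term". The treatment variable in that interaction is not defined.

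Later in the same section, the adjusted analyses are described only by their covariates: "dosing schedule, GA group, nebulizer type, mode of NIV, antenatal steroids, and presence of PDA or IVH will be included as covariates". No regression type is named and no interactions are listed. The section calls these analyses exploratory, asks for cautious reading, and concedes that subgroup comparisons may lack power. Neither passage mentions sparse cells, separation, or exact or penalized fitting.

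The layout comes from section 1.1.4.6: "allocation ratio 1:1:1:1, total subjects = 120", arranged as "3 GA strata x 2 nebulizers x 4 dosing schedule groups=24", with 5 infants per cell in Table 10. Section 1.1.10 gives a planning range ("evaluation of a failure rate of 0.25 - 0.4"). It then reports later changes: 60 infants in each upper stratum, at most 40 in Stratum I, and finally a Phase II total of 220, of which 20 places allow for screen failures.

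**The concern.** In a logistic model with a full schedule-by-GA interaction, each cell has its own fitted rate. If no infant in a cell is intubated, or every infant is, maximum likelihood has no finite estimate for at least one coefficient. The software then prints a very large odds ratio with a meaningless Wald interval, or a convergence warning. With no rule in the plan, the analyst would choose a remedy after seeing the data.

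The adjusted analysis raises a related but separate issue. It fits main effects, not cells, so its weakness is the small number of events per parameter. This tends to push log odds ratios away from zero and occasionally produces separation.

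What is at stake is whether GA-specific schedule effects and adjusted schedule effects can be reported with usable estimates and intervals. Section 1.1.10 wants Stratum I data to generate an effect-size hypothesis, and Stratum I has the smallest cells.

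**Working it through.** **The plan's own figure.** No power or event count is given for the interaction or adjusted models. The nearest figure is Table 13: 81.8% for 30 infants, 0.25 against 0.5 ("Power is for a two sided test with Type I error of 0.05"). The arcsine formula gives h = 2(asin√0.5 − asin√0.25) = 0.5236, and Φ(0.5236 × √30 − 1.96) = Φ(0.908) = 81.8%. It reproduces, so 0.25 is a fair starting rate.

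**Cell sizes.**
- Table 10: 5 infants × 2 nebulizers = 10 per schedule-by-GA cell, 12 cells.
- Current maximum: 220 − 20 = 200 infants. Stratum I is capped at 40, leaving 160, or 80 per upper stratum if split equally (an assumption). Divided by four schedules, the cells are 10/20/20.
- Low case: 20/60/60 infants, or 5/15/15 per cell. The 20 is an illustration of a shortfall in Stratum I.
- Two doses in place of four schedules at 40/80/80: 20/40/40 per cell, 6 cells.

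**Formula.** For a cell of n infants with rate p, P(empty or full) = (1−p)^n + p^n. P(at least one such cell) = 1 − ∏[1 − (1−p)^n − p^n] over all cells.

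At p = 0.25:
- n = 10: 0.75^10 + 0.25^10 = 0.0563. Twelve such cells: 1 − 0.9437^12 = 50%.
- n = 20: 0.75^20 = 0.0032. Layout 10/20/20: 1 − 0.9437^4 × 0.9968^8 = 1 − 0.793 × 0.975 = 23%.

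| Schedule × GA cells | 0.25 | 0.30 | 0.35 | 0.40 |
|---|---|---|---|---|
| 10/10/10 (Table 10) | 50% | 29% | 15% | 7% |
| 10/20/20 (current maximum) | 23% | 11% | 5% | 2.5% |
| 5/15/15 (low case) | 70% | 54% | 41% | 31% |

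**GA gradient.** Section 1.1.7.1 expects more intubation at lower GA but gives no stratum rates, so the gradients below are assumptions. At 10/20/20 the formula gives:
- 0.40/0.25/0.10: 43%
- 0.50/0.25/0.10: 42%
- 0.40/0.25/0.15: 18%
- 0.60/0.35/0.15: 17%

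**Two doses.** At 20/40/40 the chance is 0.6% at a flat 0.25 and 2.9% under 0.40/0.25/0.10.

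**Schedule by nebulizer.** Table 10 gives 8 cells of 15: 10% at 0.25 and 4% at 0.30.

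**Adjusted analysis.** Parameters: schedule 3, GA 2, nebulizer 1, NIV mode 2, steroids 1, and PDA/IVH 1 or 2, so 10 or 11.
- n = 120: 30 to 48 events at 0.25-0.40. 30/11 = 2.7 and 48/10 = 4.8 per parameter.
- n = 200: 50 to 80 events. 50/11 = 4.5 and 80/10 = 8 per parameter.

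Main-effects logistic fits were simulated with assumed covariates: steroids 80%; PDA 40/20/10% and IVH 15/5/1% by stratum; two NIV modes in each stratum; a schedule odds ratio of 0.5.
- At n = 120, separation occurred in at most about 6% of trials at flat rates and about 28% under 0.50/0.25/0.10.
- At n = 200, it occurred in at most about 5%.
- Other assumed gradients (0.60/0.35/0.15 and 0.50/0.30/0.10) gave 5-9% and about 2% respectively.
- Log odds ratios were inflated by roughly 5-17% across settings, against a few percent with Firth fitting.

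**The case against.** The strongest reply is that the risk depends on a reading the plan does not commit to. If treatment means dose, the GA cells are twice as large and the problem nearly disappears for the primary outcome. That is right, and it is why defining the contrast comes first. The singular wording of the interaction term does not settle the matter. For the dose subgroup the term has no clear meaning at all, because dose is itself the treatment and there is no untreated arm.

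Second, Table 10 has been superseded, so its 50% should not lead. That stands. The current layout gives 23% at a flat 0.25 and much less at 0.30-0.40. However, the Stratum I cells have not grown, and a shortfall there raises the risk.

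Third, the gradients are assumed. At 40/80/80, 0.40/0.25/0.10 implies an overall rate of (16 + 20 + 8)/200 = 0.22, below the planning range. The upper end of 17-43% should be read with that in mind.

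A reader might infer that all these models run on cells of about 10 and will often fail. The documents do not support this. Cells of 10 arise only for schedule by GA; the adjusted analysis fits no cells, and its model type is not stated. A reader might also infer that the efficacy conclusion is at risk. It is not: that rests on a one-sample comparison with a "historical control rate of 0.5 for need for intubation", and section 1.1.12 ties no dose-selection decision to an interaction or adjusted odds ratio.

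Finally, a likelihood-ratio test of interaction can still be computed under separation. Only the affected coefficients and their Wald intervals are lost. The exploratory label and the low-power caveat warn about missed significance; they do not address infinite estimates or estimates biased away from zero.

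**Conclusion.** The point holds in limited form and is worth considering rather than essential. The interaction analysis lacks a defined treatment contrast and a rule for empty or full cells. If the contrast is the four schedules, the chance of at least one infinite estimate in the GA interaction under the current plan is about 23% at a flat 0.25, 2.5-11% at 0.30-0.40, and 17-43% under assumed gradients. It would be about 70% at a flat 0.25 if the strata reached only 20/60/60. If the contrast is the two doses, it is about 0.6-3%. Separately, the adjusted analysis, if logistic, has 2.7-4.8 events per parameter at n = 120 or 4.5-8 at n = 200, with occasional separation and log odds ratios inflated by roughly 5-17%.

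These sizes rest on an equal split of the upper strata, Stratum I reaching its cap (except in the low case), and assumed stratum rates and covariate frequencies, none of which the documents give. Appendix IX, cited for the mock tables, was not available.

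**What to change.** Amend section 1.1.12 in four respects:

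1. State for each interaction whether treatment is the four schedules or the two doses, and say what the dose subgroup analysis compares.
2. Name the adjusted model as logistic.
3. Fit the interaction and adjusted logistic models by Firth penalized likelihood, with profile-penalized-likelihood intervals and penalized likelihood-ratio tests for interaction.
4. Print events and infants per cell beside each interaction result.

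The cost is a few lines of text and one option in SAS, which the plan already names. The downside is slight shrinkage of estimates toward zero. The method gives finite estimates but adds no information. For a single contrast of four cells of 10 at a rate of 0.25 with no true interaction, the ratio of odds ratios by maximum likelihood is infinite or zero in 21% of trials, and its 95% range among finite fits is about 0.06 to 15. The printed counts let the reader see that imprecision.
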